16.9.2. Population Pharmacokinetic (PopPK) Methodology

The primary goal of this analysis is to characterize the population pharmacokinetics of GSK2857916 and associated analytes after intravenous administration of GSK2857916 in subjects with multiple myeloma. This analysis will be performed by CPMS and reported separately.

A summary of the planned population pharmacokinetic analyses is outlined below:

- Exploratory data analyses will be performed to understand the content of the analysis dataset with respect to the anticipated models, to search for extreme values and/or potential outliers, to examine the correlation between covariates, and to assess possible trends in the data.
- Drug concentration-time data will be subjected to nonlinear mixed effects modelling using appropriate validated software to develop a population PK model.
- Based on the preliminary analysis, log-transformed drug concentration data for GSK2857916 ADC will be subjected to analysis using a two-compartment IV infusion model parameterized using either clearances and distribution volumes, micro-constants or macro-constants (A, B, ALPHA and BETA), depending on parameters to be estimated. A similar approach may be used on the data from the three analytes (ADC, total antibody, and cys-mcMMAF) together.
- Inter-individual or between-subject variability (IIV or BSV) will be initially modeled using an exponential random effects model. Random effects for clearances and volumes or A and B and BETA will be incorporated, depending on model parameterization used. If the goodness-of-fit plots reveal potential biases in the random effects model, alternative random effects models may be considered.
- An additive error model on a log-transformed data scale reflecting an exponential error residual variability model will initially be used to describe the residual variability. If the goodness-of-fit plots reveal potential biases in the residual variability model, other residual error models will be considered as appropriate.
- Covariate analysis will be performed to explore measurable sources of PK variability. Different approaches may be evaluated for covariate model building including a step-wise process consisting of a forward and a backward selection procedure and/or a full-model approach. Some of the prospectively identified covariates are listed below:
 - Continuous covariates such as age, albumin, measures of body size (e.g., body weight, body surface area, body mass index, lean body mass);
 - Categorical covariates such as gender, race, disease status, immunogenicity status, and geographic region.
- Non-parametric bootstrapping may be performed to test model robustness. The model performance may be evaluated by performing predictive check.
- Individual *post hoc* estimated PK parameters will be summarized descriptively.

- Individual subject PK parameters and exposure measures for Cycle 1 will be estimated and documented for the purposes of any subsequent exposure-response (PK/PD) analyses.

Any analyses not described *a priori* but undertaken based on emerging data will be described in detail in the report.

Data handling considerations are summarized below:

- Drug concentration data which are below the lower limit of quantification, LLQ, (NQ or BLQ) are not reported as a numeric value. Such NQ observations will be either discarded or handled in a special way. When the frequency of NQ is small, the NQ values will be excluded, since discarding NQ values in this case introduces little bias [Beal, 2001]. In situations where there are a large percentage of NQ values, other strategies which may reduce estimation bias will be considered [Beal, 2001; Hing, 2001; Ahn, 2008]. The total number and percentage of NQ values will be calculated and the rationale for the method for handling these NQ values will be documented in the final report. In situations with large number of NQ values, the predictive performance of the model will be assessed to compare the agreement between observed versus predicted proportion of samples below the LLQ.
- Concentrations that are inconsistent pharmacokinetically with the drug concentration-time profile within an individual may be considered as outliers and subsequently excluded from the dataset or analysis. Visual inspection of individual and pooled data and weighted residuals during analysis may be used to identify such outliers. Any such exclusion will be reported and discussed in the analyses summary.
- Missing data will be handled in the following way:
 - Subjects who withdrew from the study and did not provide any PK samples and do not have adequate sampling and/or covariate information will be excluded from the analysis.
 - If dosing and/or sampling times are missing, the relevant concentrations may be excluded from the analysis dataset and summarized in an exclusion listing file. Alternatively, the nominal times of the respective doses and/or samples may be utilized.
 - Imputations of any covariate value will only be performed if the variable is missing for less than 10% of the subjects. For continuous covariates, missing values for an individual subject will be imputed as the gender-specific median value for the study. Any changes to the imputation methods will be justified and documented. If the percentage of missing data is greater than 10%, the variable will only be evaluated in exploratory graphical displays and not in the population analyses. Subjects from race categories with an insufficient number for analysis (typically less than 10% of the subject population) may be re-grouped and/or defined as race “Other.”

16.10. Appendix 10: Pharmacokinetic / Pharmacodynamic Analyses

16.10.1. Pharmacokinetic / Pharmacodynamic Dataset Specification

Dataset specifications for exposure-response analyses of efficacy and of corneal toxicity are provided. Any deviations between the dataset specifications and the final datasets will be documented in the population pharmacokinetic analysis report.

For corneal events:

General Description:

1. The dataset is sorted by SUBJID
2. Three significant figures for all values except those variables which are integers.
3. Only subjects with CANCER=0 will be included in this dataset as the data for the lymphoma patients will not be fully cleaned at the time of the database cut in 4Q2018.

Column Header	Data Item	Codes	Derivation/Comments	Source data set
C	Line number/exclusion identifier	Row Number	Set to line/row number	adae
STUDY	Study ID		1 = BMA117159	adsl
USUBJID	Unique subject identifier			adsl
SUBJID	Subject identifier from source data		SUBJID = SUBJID	adsl
ID	NONMEM subject identifier		Sequential subject identifier across studies after data is sorted by SUBJID. Starting with P	
TOXTYPE	This variable is created to separate out Grade 1 toxicity from Grade 2 and higher.	1,2	2 separate datasets with one line per subject: TOXTYPE = 1 for 1 st occurrence of corneal event (CQ01NAM = Corneal Event). If CQ01NAM = missing, add 1 line for that subject.	adae
CORTOX	Presence or Absence of Corneal toxicity	0 or 1	When CQ01NAM ="Corneal Event", then CORTOX=1. When CQ01NAM =missing, then CORTOX=0.	adae
AETOXGRN	Standard Corneal Toxicity Grade	0,1,2,3		adae
WRAETOXGRN	Worst Corneal Toxicity Grade	0,1,2,3	Worst corneal toxicity grade experienced by subject throughout the entire treatment duration	adae
TTECORTOX	Time to corneal toxicity event (day)		
 • For TOXTYPE = 1 and CORTOX = 1, then TTECORTOX = AESTDY • When TOXTYPE = 1 and CORTOX = 0, then TTECORTOX = LSTCTDT – TRTSDT + 1 (TRTSDT, LSTCTDT is coming from adsl dataset) 	adae, adsl

Column Header	Data Item	Codes	Derivation/Comments	Source data set
			•	
DOAE	Duration of adverse event (days)		
This variable is for calculating the duration of adverse event following the 1st occurrence of corneal event in TOXTYPE =1
 
 • When CQ01NAM = Corneal Event and AONGO=N and AENDTF= blank, then DOAE = ADURN; • When CQ01NAM = Corneal Event and AONGO = N and AENDTF= Y/M/D, then DOAE = -99; • When CQ01NAM = Corneal Event and AONGO=Y, then DOAE = (LSTCTDT – ASTDT) + 1; • When CQ01NAM = Corneal Event and AONGO=Y, DOAE = -99 ASTDTF is not missing (has alphabet Y/M/D); • When CQ01NAM = Corneal Event and AONGO=Y, DOAE = -99 if LSTCTDT or ASTDT is missing; • When CQ01NAM = missing, then DOAE = 0; 	adae, adsl
DOAECFLCD	DOAE Censoring Flag Code	0 or 1	
When AONGO=N, then DOAECFLCD=0
 
When AONGO=Y, then DOAECFLCD=1
	adae
LNDOAE	Log of duration of adverse event		
LNDOAE = Log(DOAE);
 
When DOAE=-99, LNDOAE =-99;
 
When DOAE=0, LNDOAE=0
	adae
CUMAMTCT	Cumulative dose to TTECORTOX (mg)		
When CORTOX=1,
 
 • For adex.PARAMCD=ALTDLOSE, CUMAMTCT= Cumulative of adex.AVAL till adae.AESTDY • For corneal toxicity that occurred on dosing days, the dose on the corneal toxicity day was not included in the cumulative dose calculation. Here is the code for that: When adae.AESTDY=adex.ASTDY, then CUMAMTCT= Cumulative of adex.AVAL till (adae.AESTDY -1) 
When CORTOX=0,
 
 • CUMAMTCT= AVAL * WEIGHTBL; Get AVAL for adex.PARAMCD=CUMDOSE 	adex. adae
TAAUCCT	Time-average AUC till		The area under the plasma ADC concentration–time curve (AUC) per day	popPK output,

Column Header	Data Item	Codes	Derivation/Comments	Source data set
	TTECORTOX (AUC/day)		(AUC/day) will be derived for each patient using the available ADC dosing information, individual patient clearance values from the population pharmacokinetic model, and the time to the occurrence of the corneal toxicity.	adae
CANCER	Cancer type	0 or 1	0=Multiple Myeloma, 1=BCMA positive Lymphomas If TRT01AN = 12, then CANCER=1, else CANCER=0	adsl
AMT	Amount (in mg) of GSK2857916 given in first cycle		AMT = AVAL when PARAMCD=ALTDOSE and AVISIT= CYCLE 1 DAY 1	adex
IDOSE	GSK2857916 initial cycle dose (mg/kg)	>0	IDOSE=adex.TRT01A; strip off units	adex
CMAX	First dose Cmax of ADC – model predicted EOI concentration in Cycle 1 (ng/mL)		Individual model predicted conc. at EOI.	PopPK output
MMAFCMAX	First dose Cmax of MMAF – model predicted 24 HOURS POST-EOI in Cycle 1 (ng/mL)		Individual model predicted conc. at 24 HOURS POST-EOI in Cycle 1	PopPK output
CTAU	First dose C _{tau} of ADC– model predicted pre-dose concentration Cycle 2		Individual model predicted pre-dose conc.CYCLE 2.	PopPK output
AUC	First dose AUC(0-inf) of ADC (ug.day/mL)		First dose (mg)/Individual Clearance of ADC (L/Day)	popPK output
MMAFAUC	First dose AUC(0-inf) of MMAF (ug.day/mL)		First dose (mg)/Individual Clearance of MMAF (L/Day)	popPK output
TOTCYC	Total number of CYCLES		TOTCYC=AVAL, AVAL for adex.PARAM=Total Number of Cycles	adex
ETHN	Subject ethnicity	Same coding as CRF/Stats	Fill in ETHN in all rows for each subject If missing, ETHN = -99	adsl
AGE	Age (years)		Use value as defined by Stats;	
SEX	GENDER	0 or 1	Male = 1 Female = 0 • If sex is missing, GENDER = -99	
BWT	Baseline Weight (kg)		• Use baseline value as defined by Stats in the lab test datasets; • If not defined by Stats, set to weight measurement nearest to, but prior to, time of first dose	

Column Header	Data Item	Codes	Derivation/Comments	Source data set
			
 Only in cases where Day 1 weight is not available, but screening weight is, the screening values will be used. 	
BECOG	Baseline ECOG status	0 1 2	Fill on all rows	
ECOG	ECOG status	0 1 2	ECOG is propagated forward from the most recent measurement for all observations up to the next ECOG measurement (LOCF). Please capture the values corresponding to the PK time points.	
PRIORRX	Prior line of therapy		When addc.PARAMCD= LTXCPSCR, then PRIORRX = AVALC (Extract only the number and not the text) For AVALC = MORE THAN 10 LINES, PRIORRX=11 Fill on all rows	addc
REFRAC	Refractory status	0 = Double 1 = Other	Fill on all rows	
MMTY	Type of Multiple Myeloma	0 = Secretary 1= Non-secretory	When addc.MMYELOTY=SECRETORY, MMTY=0 When addc.MMYELOTY= NONSECRETORY, MMTY=1 If addc.MMYELOTY is missing, assign MMTY=-99 Fill on all rows.	addc
MMIGTY	Myeloma immunoglobulin	0 = IGA 1 = IGG 2 = IGM 3 = OTHER	When addc.PARAMCD=MYELOIG and AVALC=IGA, then MMIGTY =0 When addc.PARAMCD=MYELOIG and AVALC=IGG, then MMIGTY =1 When addc.PARAMCD=MYELOIG and AVALC=IGM, then MMIGTY =2 For AVALC which is not equal to IGA/ IGG /IGM, then MMIGTY=3 Fill on all rows	addc
BSTAGE	Stage at Screening	1 = I 2 = II 3 = III 4 =	When addc.PARAMCD = STAGESCR and AVALC = I, then BSTAGE = 1 When addc.PARAMCD = STAGESCR and AVALC = II, then BSTAGE = 2 When addc.PARAMCD = STAGESCR and AVALC = III, then BSTAGE = 3 When addc.PARAMCD = STAGESCR and AVALC = UNKNOWN or missing , then	addc

Column Header	Data Item	Codes	Derivation/Comments	Source data set
		UNKNOWN or missing	BSTAGE = 4 Fill on all rows	

For efficacy

General Description:

1. The dataset is sorted by SUBJID
2. Three significant figures for all values except those variables which are integers.
3. Only subjects with CANCER=0 will be included in this dataset as the data for the lymphoma patients will not be fully cleaned at the time of the database cut in 4Q2018.

Column Header	Data Item	Codes	Derivation/Comments	Source data set
C	Line number/exclusion identifier	Row Number	Set to line/row number	
STUDY	Study ID		1 = BMA117159	adsl
SUBJID	Subject identifier from source data		SUBJID = SUBJID	adsl
ID	NONMEM subject identifier		Sequential subject identifier across studies after data is sorted by SUBJID. Starting with P	derived
PFSCFLCD	PFS Censoring Flag Code	0 or 1	For PARAMCD=PFS_D, CNSR value is assigned to PFSCFLCD 0=Event 1=Censor	adtte
PFSD	PFS (Days)		For PARAMCD=PFS_D, AVAL value is assigned to PFSD When AVAL is missing for PFS_D, then PFSD = -99.	adtte
PFSM	PFS (Months)		For PARAMCD=PFS_M, AVAL value is assigned to PFSM When AVAL is missing for PFS_M, then PFSM = -99.	adtte
PFSY	PFS (Years)		For PARAMCD=PFS_D, (AVAL/365) value is assigned to PFSY When AVAL is missing for PFS_Y, then PFSY = -99.	derived
TTRCFLCD	TTR Censoring Flag Code	0 or 1	For PARAMCD=TTR_D, Assign 1 to TTRCFLCD. For subjects where TTR_D is missing, assign 0 to TTRCFLCD.	adtte
TTRD	TTR (Days)		For PARAMCD=TTR_D, AVAL value is assigned to TTRD. For subjects where TTR_D is missing, assign PFSD to TTRD.	adtte

Column Header	Data Item	Codes	Derivation/Comments	Source data set
TTRM	TTR (Months)		For PARAMCD=TTR_M, AVAL value is assigned to TTRM. For subjects where TTR_M is missing, assign PFSM to TTRM.	adtte
TTRY	TTR (Years)		For PARAMCD=TTR_D, (AVAL/365) value is assigned to TTRY. For subjects where TTR_D is missing, assign PFSY to TTRY.	derived
DORCFLCD	DOR Censoring Flag Code	0 or 1	For PARAMCD=DOR_D, CNSR value is assigned to DORCFLCD 0=Event 1=Censor Assign "." for missing.	adtte
DORD	DOR (Days)		For PARAMCD=DOR_D, AVAL value is assigned to DORD. For subjects where DOR_D is missing, assign "." When TTRCFLCD=0, then DORD = 0	adtte
DORM	DOR (Months)		For PARAMCD=DOR_M, AVAL value is assigned to DORM. For subjects where DOR_M is missing, assign "." When TTRCFLCD=0, then DORM = 0	adtte
DORY	DOR (Years)		For PARAMCD=DOR_D, (AVAL/365) value is assigned to DORY For subjects where DOR_Y is missing, assign "." When TTRCFLCD=0, then DORY = 0	derived
ORDRESP		0,1,2,3,4,5,6	For PARAMCD=BCRSP, assign 0 for PD 1 for SD 2 for MR 3 for PR 4 for VGPR 5 for CR 6 for sCR	adrs
MAXPRED			Obtain AVAL for PARAMCD=MAXPRED. When AVAL is missing, MAXPRED = -999	adrs
RESPRATIO	Transform MAXRED to a ratio to baseline		RESPRATIO = $\max((100+\text{MAXRED})/100, 0.001)$ 
 When MAXRED is missing, MAXRED = -999 and RESPRATIO= -99 When MAXRED is less than -100 e.g. -100.15, RESPRATIO = negative (It is negative but greater than -8.99), then update RESPRATIO = 0.001 When MAXRED is equal to -100, RESPRATIO = 0, then update RESPRATIO = 0.001 	adrs,derived
RSPTYP	Response Type	1,2,3	1 for Serum M-Protein 2 for Serum FLC	adrs

Column Header	Data Item	Codes	Derivation/Comments	Source data set
			3 for Urine M-Protein	
CUMAMTP	Cumulative dose to progression (mg)		
This is needed to derive Time-average AUC till progression. For adtte.PARAMCD=PFS_D, adex.PARAMCD=ALTDOSE, CUMAMTP= Cumulative of adex.AVAL starting from adtte.STARTDT and ending at adtte.ADT
 
For progression that occurred on dosing days, the dose on the progression day was not included in the cumulative dose calculation. Here is the code for that: When adtte.ADT = adex.ASTDT at the last dose for that subject, then CUMAMTCT= Cumulative of adex.AVAL starting from adtte.STARTDT and ending at (adtte.ADT -1)
	adex, adtte
TAAUCP	Time-average AUC till progression (AUC/day)		The area under the plasma ADC concentration–time curve (AUC) per day (AUC/day) will be derived for each patient using the available ADC dosing information, individual patient clearance values from the population pharmacokinetic model, and the time to the occurrence of the PFS	popPK output, adtte
CUMAMTR	Cumulative dose to Response (mg)		
This is needed to derive Time-average AUC till response. For adtte.PARAMCD=TTR_D, • adex.PARAMCD=ALTDOSE, CUMAMTR= Cumulative of adex.AVAL starting from adtte.STARTDT and ending at adtte.ADT
 
• For response that occurred on dosing days, the dose on the response day was not included in the cumulative dose calculation. Here is the code for that: When adtte.ADT = adex.ASTDT at the last dose for that subject, then CUMAMTCT= Cumulative of adex.AVAL starting from adtte.STARTDT and ending at (adtte.ADT -1)
 
When TTRCFLCD=0 (i.e. subjects who did not respond), then CUMAMTR=TOTAMT
	adex, adtte
TAAUCR	Time-average AUC till response (AUC/day)		The area under the plasma ADC concentration–time curve (AUC) per day (AUC/day) will be derived for each patient using the available ADC dosing information, individual patient clearance values from the population pharmacokinetic model, and the time to the occurrence of the response	popPK output, adtte
AMT	Amount (in mg) of GSK2857916 given in first cycle		AMT = AVAL when PARAMCD=ALTDOSE and AVISIT= CYCLE 1 DAY 1	adex
IDOSE	GSK2857916 initial cycle dose (mg/kg)	>0	IDOSE=adex.TRT01A; strip off units	adex
CMAX	First dose Cmax of			PopPK

Column Header	Data Item	Codes	Derivation/Comments	Source data set
	ADC – model predicted EOI concentration in Cycle 1 (ng/mL)		Individual model predicted conc. at EOI.	output
MMAFCMAX	First dose C _{max} of MMAF – model predicted 24 HOURS POST-EOI in Cycle 1 (ng/mL)		Individual model predicted conc. at 24 HOURS POST-EOI in Cycle 1	PopPK output
CTAU	First dose C _{tau} of ADC– model predicted pre-dose concentration Cycle 2		Individual model predicted pre-dose conc.CYCLE 2.	PopPK output
AUC	First dose AUC(0-inf) of ADC (ug.day/mL)		First dose (mg)/Individual Clearance of ADC (L/Day)	popPK output
MMAFAUC	First dose AUC(0-inf) of MMAF (ug.day/mL)		First dose (mg)/Individual Clearance of MMAF (L/Day)	popPK output
TOTCYC	Total number of CYCLES		TOTCYC=AVAL, AVAL for adex.PARAM=Total Number of Cycles	adex
CANCER	Cancer type	0 or 1	0=Multiple Myeloma, 1=BCMA positive Lymphomas If TRT01AN = 12, then CANCER=1, else CANCER=0	adsl
ETHN	Subject ethnicity	Same coding as CRF/Stats	Fill in ETHN in all rows for each subject If missing, ETHN = -99	adsl
AGE	Age (years)		Use value as defined by Stats;	adsl
SEX	GENDER	0 or 1	Male = 1 Female = 0 • If sex is missing, GENDER = -99	adsl
BWT	Baseline Weight (kg)		• Use baseline value as defined by Stats in the lab test datasets; • If not defined by Stats, set to weight measurement nearest to, but prior to, time of first dose • Only in cases where Day 1 weight is not available, but screening weight is, the screening values will be used.	adsl
BECOG	Baseline ECOG status	0 1 2	Fill on all rows	adqs
ECOG	ECOG status	0 1 2	ECOG is propagated forward from the most recent measurement for all observations up to the next ECOG measurement (LOCF). Please capture the values corresponding to the PK time points.	adqs
PRIORRX	Prior line of therapy		When addc.PARAMCD= LTXCPSCR, then	addc

Column Header	Data Item	Codes	Derivation/Comments	Source data set
			PRIORRX = AVALC (Extract only the number and not the text) For AVALC = MORE THAN 10 LINES, PRIORRX=11 Fill on all rows	
REFRAC	Refractory status	0 = Double 1 = Other	Fill on all rows	
MMTY	Type of Multiple Myeloma	0 = Secretory 1 = Non-secretory	When addc.MMYELOTY=SECRETORY, MMTY=0 When addc.MMYELOTY=NONSECRETORY, MMTY=1 If addc.MMYELOTY is missing, assign MMTY=-99 Fill on all rows.	addc
MMIGTY	Myeloma immunoglobulin	0 = IGA 1 = IGG 2 = IGM 3 = OTHER	When addc.PARAMCD=MYELOIG and AVALC=IGA, then MMIGTY =0 When addc.PARAMCD=MYELOIG and AVALC=IGG, then MMIGTY =1 When addc.PARAMCD=MYELOIG and AVALC=IGM, then MMIGTY =2 For AVALC which is not equal to IGA/ IGG /IGM, then MMIGTY=3 Fill on all rows	addc
BSTAGE	Stage at Screening	1 = I 2 = II 3 = III 4 = UNKNOWN or missing	When addc.PARAMCD = STAGESCR and AVALC = I, then BSTAGE = 1 When addc.PARAMCD = STAGESCR and AVALC = II, then BSTAGE = 2 When addc.PARAMCD = STAGESCR and AVALC = III, then BSTAGE = 3 When addc.PARAMCD = STAGESCR and AVALC = UNKNOWN or missing , then BSTAGE = 4 Fill on all rows	addc

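### The time-averaged exposure columns in SAP 16.10.1 use windows set by the outcome, and the cumulative-dose-to-response code contradicts its own rule; both can create a spurious exposure-response relation if those columns are modelled

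*SAP*

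**What the plan says.** **Corneal dataset (SAP 16.10.1).** For subjects with an event, "For TOXTYPE = 1 and CORTOX = 1, then TTECORTOX = AESTDY", the study day of onset. For subjects without one, "When TOXTYPE = 1 and CORTOX = 0, then TTECORTOX = LSTCTDT" minus the first-dose date, plus 1. The dose to the event leaves out a dose given on the event day: "the dose on the corneal toxicity day was not included in the cumulative dose calculation". Subjects without an event receive their whole cumulative dose: "CUMAMTCT= AVAL * WEIGHTBL; Get AVAL for adex.PARAMCD=CUMDOSE". The time-averaged AUC, TAAUCCT, is then derived from dosing, "individual patient clearance values from the population pharmacokinetic model, and the time to the occurrence of the corneal toxicity".

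**Efficacy dataset (SAP 16.10.1).** For the cumulative dose to response, CUMAMTR, the text says: "For response that occurred on dosing days, the dose on the response day was not included in the cumulative dose calculation". The code line that follows reads: "When adtte.ADT = adex.ASTDT at the last dose for that subject, then CUMAMTCT= Cumulative of adex.AVAL", summed to the day before. The same code line stands under CUMAMTP, the cumulative dose to progression. Non-responders take a total dose, TOTAMT, and their time to response is set to their PFS time. On the response flag the table says: "For PARAMCD=TTR_D, Assign 1 to TTRCFLCD". Subjects without a response time get 0.

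**Models (SAP 16.10.2.1).** Logistic regression, ordered logistic regression and Kaplan-Meier plots are planned against exposure. No exposure metric is named as primary. Both datasets also hold first-dose metrics (IDOSE, AMT, CMAX, CTAU, AUC and the cys-mcMMAF counterparts), and 16.9.2 says that Cycle 1 exposure measures are to be produced for exposure-response work.

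**The concern.** An exposure metric should not depend on whether the subject had the outcome. TAAUCCT does. Days off treatment enter the denominator only for subjects without a corneal event, so their average exposure is pulled down. Those days can be many. In the Part 2 myeloma schedule (16.2.3.1, footnote 29) survival follow-up runs to one year after the last subject's last dose.

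In the efficacy dataset, a dose given after the response was assessed can count as exposure leading to it. Assessments on dosing days precede the infusion (16.2.3.1, footnote 1), myeloma tests are drawn at the start of each cycle, and a response carries the visit date (16.5.5). Responses will therefore often fall on dosing days, and most responders will go on to further doses. The code's exception would then rarely apply.

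Both mechanisms push the same way: more toxicity and more response at higher apparent exposure, with no true relation.

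**Working it through.** The SAP gives no error rate or sample size for these analyses, so there is no planned figure to reproduce. The check is arithmetic on the SAP rules, then a simulation under no true effect.

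**1. Corneal window, equal dose and clearance.** Doses per day = number of doses / TTECORTOX, with a 21-day cycle (SAP 2.3).

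- On treatment: 1/21 = 0.048.
- Event on day 40 after 2 doses: 2/40 = 0.050.
- No event, 4 cycles (84 days), then 0, 90, 180 or 365 days to last contact: 4/84 = 0.048, 4/174 = 0.023, 4/264 = 0.015, 4/449 = 0.009.
- Event against non-event: 1.05, 2.2, 3.3 and 5.6 times.
- No event, 6 cycles (126 days) plus 365 days: 126/(126 + 365) = 126/491 = 0.26 of the on-treatment value.

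**2. Response-day dose.** Response at Cycle k Day 1, treatment continued: the code counts k doses, the text k − 1.

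| First response | Code | Text | Ratio |
|---|---|---|---|
| C2D1 (day 22) | 2/22 = 0.091 | 1/22 = 0.045 | 2.0 |
| C3D1 (day 43) | 3/43 = 0.070 | 2/43 = 0.047 | 1.5 |
| C4D1 (day 64) | 4/64 = 0.063 | 3/64 = 0.047 | 1.33 |

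**3. Null simulation.** Exposure has no effect on either outcome; columns are built by the SAP rules; logistic score test on log exposure at two-sided 0.05; 2,000 corneal and 1,000 response runs. Assumptions not in the SAP: clearance CV 30%, one dose level, median treatment 126 days, median corneal onset 42 days (about 79% incidence), response first seen at C2 to C5 Day 1 in 50/25/15/10% of responders, response rate 20-60%.

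False-positive rate for TAAUCCT:

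| Mean off-treatment follow-up | Onset any day, n=40 / n=70 | Onset dated at pre-dose exam, n=40 / n=70 |
|---|---|---|
| None | 46% / 84% | 7% / 7% |
| 30 days | 99% / 100% | 97% / 100% |
| 90 days or more | 100% / 100% | 100% / 100% |
| Window closed at end of last dosing interval | 37-40% / 77-80% | 4-6% / 5-6% |

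At 30 days and n=40, the rate was 79% with clearance CV 50% and 99% with CV 20%. Cycle 1 AUC gave 4-6% throughout. For response, the code as written gave 97-100%, with a responder-to-non-responder median ratio near 1.67; the rule in the text gave 4-6%.

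The last row of the table shows that closing the window at the end of treatment is not enough. An event soon after a dose still has a high average. For example, an event on day 26, after doses on days 1 and 22, gives 2/26 = 0.077 against 0.048.

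**4. Sensitivity to dose spread.** Part 1 doses run from 0.03 to 4.6 mg/kg (SAP 5.1), a 153-fold range. With half of 70 subjects spread over those levels (allocation assumed) and last contact 0-90 days after treatment, false positives were 53-99.8% and the c-index 0.65-0.78. With last contact within 30 days and onset dated at the pre-dose exam, false positives were 10%.

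**The case against.** Several stronger readings are tempting, and the SAP does not support them.

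- **That the planned models will show a false relation.** Section 16.10.2.1 speaks only of exposure measures. The metrics that 16.9.2 earmarks for this work are Cycle 1 ones, and these are clean. This stands. But the time-averaged columns are built for these datasets, and nothing keeps them out of the models.
- **That dose or schedule choice is at stake.** No section says so. Escalation rests on the N-CRM and all available data (3.1.1), Part 2 is already at one dose, and weekly dosing was not explored. Exposure-response is an exploratory objective, reported separately. This stands.
- **That separation of events from non-events is near perfect.** With no dose variation and last contact up to 90 days after treatment, one simulation gave a c-index of 0.94 and p<0.05 in every run. Step 4 shows a weaker effect once Part 1 doses enter. Long follow-up also does not apply to everyone: Part 1 had a 3-month off-study contact, and earlier completers needed re-consent.
- **That the plan means to count the response-day dose.** Its text says the opposite. CUMAMTCT belongs to the corneal dataset, and the identical line under CUMAMTP suggests a copying slip.
- **That the response flag adds bias.** TTRCFLCD runs opposite to PFSCFLCD and DORCFLCD (0 = event, 1 = censor), but it is used consistently and the CUMAMTR row explains it. It does not alter exposure.
- **That non-events must be censored at the last eye exam.** CORTOX comes from adverse events, which are recorded continuously and which 8.7 separates from corneal signs on examination. That date is debatable.

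**Conclusion.** The point holds for the time-averaged columns. TAAUCCT has an averaging window set by the outcome, and the CUMAMTR code contradicts its text and names the wrong target. The 0.26 dilution and the 2.0-, 1.5- and 1.33-fold inflation follow from the SAP rules for the cases stated.

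How often this yields a false finding depends on off-treatment follow-up, the dating of onset and the dose spread, none of which the SAP fixes. In the corneal simulations it ranged from about nominal (7%, no off-treatment time and onset dated at the pre-dose exam) to certain (90 days or more at one dose level). The code under CUMAMTP has the same fault but does less harm, because progression usually falls at the last dose.

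The damage is limited to exploratory analyses, and occurs only if a time-averaged metric is modelled. The primary safety analysis and ORR are untouched. The edits are still worth making, because the bias is avoidable and the code contradiction needs correcting in any case.

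**What to change.** 1. In 16.10.2.1, name Cycle 1 CMAX, CTAU and AUC as the primary exposure metrics.
2. If time-averaged AUC is kept, make it secondary. Compute it to a common landmark in all subjects, or use it as a time-varying covariate in a time-to-event model. Never divide by off-treatment follow-up. Of these options only the Cycle 1 metric was simulated.
3. In CUMAMTR, and in the matching CUMAMTP text, remove the condition that limits the exclusion to the subject's final dose, and assign the result to CUMAMTR or CUMAMTP, not CUMAMTCT.
4. Optional, for consistency only: relabel TTRCFLCD as a response indicator. Alternatively, recode it to 0 = event, 1 = censor and update all four rules that depend on it (DORD, DORM, DORY and CUMAMTR). Updating only some would give responders a zero duration of response or their total dose.

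The cost is a set of edits to the dataset specification. The Cycle 1 metrics already have columns; a landmark or time-varying metric would need some programming. The downside is that time-averaged exposure, which reflects dose reductions and delays, becomes secondary.
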